1. PURPOSE OF THE STUDY

a. Brief Summary

After patients with chronic rhinosinusitis (CRS) undergo sinus surgery, they are typically instructed to take oral steroids for several days to weeks. However, there is limited data to suggest this is a beneficial practice, and oral steroids have been shown to have significant and unpleasant side effects. This study will investigate whether there is truly evidence based utility to the use of steroids after sinus surgery

b. Objectives

Chronic rhinosinusitis is a disease that affects an estimated 13% of the adult population. Patients with this disease suffer from reduced quality of life, impaired sleep, fatigue, acute infections, and chronic pain. Healthcare expenditures for CRS are estimated at \$8.6 billion annually, with the majority of costs arising from repetitive physician visits, emergency department encounters, and medications. Despite its prevalence, relatively little is understood about optimal medical therapy in the post-operative period. As described above, oral steroids are routinely prescribed after sinus surgery based on anecdotal data and expert opinion rather than convincing, randomized controlled data. The aim of conducting this study, therefore, is to determine if oral steroids have a role in the peri-operative treatment of patients with CRS. This study would contribute a wealth of important data to the field of Rhinology and the management of CRS. The role of steroids in the peri-operative period would be further elucidated, providing randomized controlled data with which providers may make informed therapeutic decisions. In summary, the results of this study have significant potential to influence current practice and management guidelines.

c. Rationale for Research in Humans

The purpose of the study is to test the efficacy of of a medication in individuals with CRS, which is not a disease known to be accurately duplicated in any other model.

2. STUDY PROCEDURES

a. Procedures

Screening: Patients who have been recommended to undergo endoscopic sinus surgery by our department will be recruited for the study and informed of its purpose pre-operatively. SNOT22 scores (a quality of life survey well established in Rhinology) and Lund-Kennedy endoscopic exam scores (an quantitative clinical assessment of disease severity) will be recorded in their medical records. This is the same protocol performed for all patients seen in our clinic regardless of their enrollment in the study. Randomization and Treatment Groups: The patients that wish to participate will be randomized into two treatment arms by our nurse practitioner based on a random number generator. They will receive one of the following post-operative regimens: 1) oral steroid (treatment) + steroid spray (treatment) 2) oral placebo (control) + steroid spray (treatment) These medications will be manufactured and packaged by an independent compounding pharmacy, and prescribed by our nurse practitioner at the preoperative visit. Patients will begin their therapy on the first post-operative day. All oral steroid regimens will be given in our institution's standard 12 days taper, while topical steroids will be delivered via a metered dose nasal spray bottle for two weeks. All study patients will receive identical perioperative antibiotic therapy. We do not anticipate these medications to be an inconvenience to study patients as all proposed interventions are not different from routine post-operative care. In addition, patients undergoing surgery will have already trialed these medications as part of their pre-operative medical therapy. Surgery: Routine endoscopic sinus surgery will be performed per our institution's standard protocol. In this step there will be no difference in treatment from those patients not enrolled in the study. Post-Operative Care: At this point, patients will begin therapies according to the treatment arm to which they have been randomized. Study patients will attend post-operative appointments at identical time points to non-study patients. These will take place at the following intervals: Post-operative visit 1: 1-2 weeks Post-operative visit 2: 6-8 weeks Post-operative visit 3: 12-16 weeks Post-operative visit 4: 6 months Experimental therapy will finish after 2 weeks. At this visit, all patients will then be maintained on intranasal steroid spray and nasal saline irrigations, which is the commonly employed therapeutic standard. Thereafter, patients will, per standard protocol, be followed on an observational basis depending on the severity of symptoms and response to treatment. At each visit, as is done for all individuals, SNOT-22 and LundKennedy endoscopic exam scores will be repeated and recorded.

b. Procedure Risks

This study does not seek to evaluate a novel research procedure. Rather, we endeavor to determine if a procedure already in place nearly universally is, in fact, beneficial, as there is a

distinct lack of evidence of suggest so. Overall, we are investigating a procedural method that will have fewer side effects than the currently accepted practice.

c. Use of Deception in the Study

NA

d. Use of Audio and Video Recordings

NA

e. Alternative Procedures or Courses of Treatment

All reasonable alternatives are included as a treatment arm in this study. There is no standard of care that is being withheld from patients in any group.

f. Will it be possible to continue the more (most) appropriate therapy for the participant(s) after the conclusion of the study?

Yes, patients will stop all experimental therapies at the 2 week mark. They will then be placed on the typical post-operative regimen, which includes a nasal steroid spray and twice daily saline irrigations. They will continue to be followed in our clinic after the 4 week mark, and their therapies tailored to their current symptoms and the endoscopic appearance of the nasal cavity.

g. Study Endpoint(s)

Currently, our post-operative protocol dictates that patients will be seen in clinic at 1 week, 3 weeks, and 6 weeks after surgery. We will only slightly alter this timeline for study patients. At the 2 week appointment, all experimental therapies will be completed. Patients will then be started on intranasal steroid sprays and saline irrigations so as not to deviate for an extended period from currently accepted practices. We will use the final scheduled appointment at 4 weeks after surgery as the official end point for comparison of treatment arms. Additionally, outcomes evaluated will be the symptom questionnaire and the endoscopic exam score at each visit. If, during the course of follow up, one regimen proves to be clearly superior to another, the study will be terminated and patients will receive the optimal therapy. By power analysis, we require 50 patients to achieve statistical significance. If there is a clearly optimal therapy determined in these first 50 patients, we will end our research at that time. All patients will continue to be followed beyond 4 weeks depending on symptom severity and response to treatment

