5. PARTICIPANT POPULATION

a. Planned Enrollment

Based on a current rate of 12-15 endoscopic sinus surgeries weekly, as well as allowing for a significant percentage of patients who do not desire to participate in the study, we anticipate between 80 and 100 patients to enroll. The study will be conducted only at Stanford Hospitals and Clinics. Participants will be those with CRS with and without polyps who have been recommended and consented for endoscopic sinus surgery. These participants will be used because they suffer from the specific disease for which we endeavor to research alternative therapies

b. Age, Gender, and Ethnic Background

We will recruit patients >18 that are able to provide consent. There will be no gender or ethnic exclusions.

c. Vulnerable Populations

NA

d. Rationale for Exclusion of Certain Populations

Children will not be included in this study as it is not typical for endoscopic sinus surgery to be performed in this population. It is rare for them to develop the extent of disease that would require surgical intervention, and surgery, in fact, is often avoided as the sinuses have not fully developed in the pediatric population. Furthermore, they are unable to provide their own informed consent to participate in this trial.

e. Stanford Populations

NA

f. Healthy Volunteers

NA

g. Recruitment Details

Recruitment will be invitation only from the patient population seen in our Rhinology clinics. Patients will first be evaluated by our providers. If, based on that evaluation, endoscopic sinus surgery is recommended to them and they meet inclusion criteria, they will then be informed of the study and its purpose and importance. After this has been discussed, patients will be invited to participate if they so choose. Our nurse practitioner performs all study introductions and obtains consent. If there are any questions, Rhinology providers are always available for consultation. We do not intend to advertise to nor recruit within the general public. There will be no recruitment materials.

h. Eligibility Criteria

i. Inclusion Criteria

Age > 18
Able to provide informed consent
Chronic rhinosinusitis with or without nasal polypsis based on published diagnostic criteria
Patients undergoing endoscopic sinus surgery

ii. Exclusion Criteria

Age
Aspirin exacerbated respiratory disease
Allergic fungal sinusitis
Cystic fibrosis
Immunosuppression
Chronic steroid use
Steroid use within 30 days prior to surgery

i. Screening Procedures

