Perioperative Oral Steroids for Chronic Rhinosinusitis Without Polyps

Statistical Analysis Plan

NCT02748070

July 2, 2020

[name], Principal Investigator
Stanford University
Stanford, California 94305

The planned sample size was 75 patients. By power analysis, we required 50 patients to achieve statistical significance. We collected outcome measures of SNOT-22 and Lund-Kennedy endoscopy scores at the following time points: preoperative baseline, and postoperatively at 1 week, 1 month, 3 months, and 6 months.

All statistical analyses were performed using Stata 15 (Stata Statistical Software: Release 15; StataCorp LP, College Station, Texas). SNOT-22 total scores, SNOT-22 subdomain scores, Lund-Kennedy endoscopic scores, and adverse effects were compared between prednisone and placebo groups at each time point using t-tests.

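### The protocol enrols CRS with and without polyps but the SAP title says without; if both groups are analysed, t-tests that ignore polyp status lose precision

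*Protocol*

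**What the plan says.** **Assignment.** Protocol section 2a has patients "randomized into two treatment arms by our nurse practitioner based on a random number generator". Nothing there or elsewhere describes blocks, strata or an allocation ratio.

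**Population in the protocol.** Section 5a: "Participants will be those with CRS with and without polyps who have been recommended and consented for endoscopic sinus surgery". The inclusion criteria in section 5h agree: "Chronic rhinosinusitis with or without nasal polypsis based on published diagnostic criteria". Polyp status is therefore part of the entry diagnosis and is known before assignment.

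**Population in the SAP.** The title reads "Perioperative Oral Steroids for Chronic Rhinosinusitis Without Polyps". The body of the SAP does not define the analysed population.

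**Analysis.** According to the SAP, SNOT-22 totals and subdomains and Lund-Kennedy scores "were compared between prednisone and placebo groups at each time point using t-tests". It names no covariate, stratum or subgroup. Both scores are also collected at preoperative baseline.

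**Size.** Protocol section 2g: "By power analysis, we require 50 patients to achieve statistical significance". SAP: "The planned sample size was 75 patients". Protocol section 5a expects 80 to 100 to enrol.

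**The concern.** A trial that enrols two diagnostic groups and ignores the distinction at both assignment and analysis can lose precision in two linked ways. The arms may differ by chance in their share of polyp patients, and any outcome difference between the groups stays in the error term. At 50 to 75 patients such chance differences are common, and section 2g allows the trial to end on the evidence of the first 50.

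The SAP title adds a prior problem. If the analysis covers only patients without polyps, it addresses a different population from the one the protocol enrols, and the polyp adjustment has no role. A reader cannot tell from the documents which situation applies.

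**Working it through.** **The plan's own figure.** The 50 patients cannot be reproduced, because no alpha, sidedness, power, effect size or SD is given. Back-solving with two equal arms, two-sided 5% and 80% power gives d = (1.960 + 0.842) × √(2/25) = 0.79 SD.

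**Assumptions, since the documents are silent.** Let p be the share with polyps (20% to 60%). Let g be the outcome gap between the two groups in within-group SDs (0.3 to 1.0).

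**Step 1: chance imbalance under simple randomisation.** The SD of the between-arm difference in polyp share is 2√(p(1−p)/N).

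- p = 0.4, N = 75: 2√(0.24/75) = 0.113. A difference of 15 points or more is 1.33 SDs, probability 18.5% (19.1% by simulation).
- p = 0.4, N = 50: 2√(0.24/50) = 0.139. This is 1.08 SDs, probability 27.9% (28.1% by simulation).
- p = 0.2, N = 75: 2√(0.16/75) = 0.092. This is 1.62 SDs, probability 10.4%.

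**Step 2: what such an imbalance does.** A 15-point difference moves the arm comparison by 0.15g, which is 0.045 SD at g = 0.3 and 0.15 SD at g = 1.0. The standard error at N = 75 is about 2/√75 = 0.23 within-group SD, so the shift is 0.2 to 0.65 of a standard error.

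**Step 3: variance explained by polyp status.** R² = p(1−p)g² / (1 + p(1−p)g²).

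- Smallest, p = 0.2 and g = 0.3: 0.0144/1.0144 = 1.4%.
- p = 0.2, g = 0.5: 0.04/1.04 = 3.8%.
- p = 0.4, g = 1.0: 0.24/1.24 = 19.4%.
- Largest, p = 0.5 and g = 1.0: 0.25/1.25 = 20.0%.

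At p = 0.5, adjusting is worth N × R² patients. With N = 50 the same precision needs 48.9 (g = 0.3), 47.1 (0.5), 43.1 (0.8) or 40.0 (1.0).

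**Step 4: simulated power and type I error.** N = 50, p = 0.5, true effect 0.8 within-group SD for power, 10,000 runs per setting.

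| Gap g | Power: simple, t-test | Power: simple, covariate | Power: stratified blocks, covariate | Type I: simple, t-test | Type I: stratified blocks, t-test |
|---|---|---|---|---|---|
| 0.3 | 77.3% | 77.5% | 79.0% | 4.7% | 4.8% |
| 0.5 | 75.9% | 77.5% | 79.0% | 4.7% | 4.4% |
| 0.8 | 72.0% | 77.5% | 79.0% | 4.7% | 3.6% |
| 1.0 | 68.8% | 77.5% | 79.0% | 4.8% | 2.9% |

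Three results follow. The t-test under simple randomisation keeps its error rate. Except at the smallest gap, most of the recoverable power comes from the covariate; stratifying then adds about 1.5 points. Stratifying without adjusting makes the t-test conservative. Blocks of 4 stratified by polyp status cut the SD of the share difference from 0.14 to 0.026, but not to zero.

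**Step 5: the baseline score.** A baseline correlation of ρ removes ρ² of the variance. An assumed ρ = 0.5 gives 25%, more than polyp status gives anywhere in the range above.

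**The case against.** The strongest objection is the SAP title. If only patients without polyps are analysed, polyp status is constant, so there is no polyp imbalance to correct and no polyp term to estimate. That stands, and it is why the adjustment is conditional. It does not dispose of the point, because sections 5a and 5h of the protocol still admit both groups and nothing reconciles the two documents. If a non-polyp subset were drawn from a mixed randomised sample, its arm split would not have been controlled by any described procedure. That matters little: with an assumed 45 such patients, a split of 27:18 or worse has probability 23%, but it costs only 4% of the information (27 × 18/45 = 10.8 against 11.25).

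A reader might infer three stronger things that the documents do not support.

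- *That assignment was unrestricted.* The protocol is silent on blocking. A random number generator can also produce blocked or stratified lists.
- *That chance imbalance biases the comparison or inflates false positives.* Under simple randomisation it is random error already in the t-test's standard error. The shift in step 2 and the variance in step 3 are one cost, not two.
- *That stratified blocks and a covariate would eliminate the problem.* They reduce it. Blocks leave some imbalance, and the covariate removes only what polyp status explains.

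It is also fair to object that the gain may be small. At a gap of 0.3 to 0.5 SD and p = 0.5, adjustment is worth about 1 to 3 patients in 50. Uneven arm sizes matter little too: a 30:20 split or worse has probability 20% at N = 50, but 30:20 costs 4% (30 × 20/50 = 12 against 12.5). Finally, the SAP is dated July 2, 2020 and written in the past tense, so a change to randomisation may come too late.

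**Conclusion.** The point holds in a limited, conditional form. The protocol and the SAP title name different populations and must be reconciled. If both groups are analysed, ignoring polyp status gives up precision without making the comparison invalid. The loss is about 1% to 20% of the variance for 20% to 60% with polyps and a gap of 0.3 to 1.0 SD. Both ranges are assumptions, and the lower end is negligible. The imbalance probabilities of 19% at N=75 and 28% at N=50 further assume simple randomisation and 40% with polyps.

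If only patients without polyps are analysed, the reconciliation is still needed but the polyp adjustment falls away. Because the SAP reads as written after data collection, the model is the change most likely to be usable.

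**What to change.** 1. State the analysed population in the same terms in protocol sections 5a and 5h and in the SAP, title included.
2. If both groups are included, replace the t-tests on SNOT-22 and Lund-Kennedy scores with a linear model containing treatment, polyp status and the baseline value of the same score. Show the arm effect by polyp status as supportive only.
3. If enrolment is still open, use a list prepared in advance in permuted blocks, stratified by polyp status, and describe it in section 2a. Keep polyp status in the model, because stratifying alone makes the t-test conservative. If enrolment is closed, change only the model and state in section 2a how the list was actually generated.
4. If only patients without polyps are analysed, omit the polyp term.

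The cost is one extra field at assignment and one or two degrees of freedom. No new data are needed: polyp status is part of the diagnosis and the baseline scores are already collected.

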support its use (1). Therefore, this almost universal current practice is perpetuated by anecdotal data and expert opinion. Furthermore, systemic steroids are associated with known significant side effects and potential drug interactions. These may be severe and include but are not limited to high blood pressure, hyperglycemia and diabetes, adrenal suppression, weight gain, glaucoma, osteoporosis, fluid retention, gastrointestinal bleeding, ulcers, and mood changes (2). Thus, oral steroids potentially pose a significant risk, have unproven benefit, and are not appropriate for repeated or longterm use – an unfortunate obstacle in treating a chronic disease. Recently, steroids dissolved in a saline irrigant have been increasingly used and proven to be effective in the routine management of CRS. Furthermore, several studies have suggested the utility and safe side effect profile of these medications; however, the data supporting their use as a perioperative treatment is distinctly lacking. While the data to support the utility of topical steroids in the treatment of CRS is evident, relatively few groups have explored topical steroid irrigations specifically as a peri-operative intervention. Fandino et al conducted a meta-analysis of 13 randomized clinical trails and cohort studies examining the use of topical steroids delivered via drops, sprays, nebulizers, or irrigations for patients with CRS with nasal polyps who had previously undergone endoscopic sinus surgery. According to his analysis, intra-nasal corticosteroids had a significant beneficial effect on symptom scores and a reduction in polyp scores. Additionally, the use of INCS decreased the rate of polyp recurrence, and did not alter adrenocorticotrophic hormones post-intervention, suggesting the intra-nasal delivery method to carry less risk than the oral version (3). Snidvongs et al conducted a study with 111 patients and reported significant improvement in symptom scores and endoscopy scores over those who did not receive postoperative topical steroids (4). Jang et al retrospectively evaluated 60 patients postsurgically who were treated with topical steroid deliveries and showed a significant decrease in quality of life and endoscopy scores after patients stopped their treatments (5). In summary, the data supporting the use of steroids in patients with CRS immediately after endoscopic sinus surgery is sparse. We, therefore, seek to more definitively elucidate the role and utility of steroid treatment in the peri-operative period. Furthermore, per our review of the literature, there has been no direct comparison of the traditional oral regimen to topical therapy (nasal spray). Could these be proven equally effective, topically delivered steroids may be considered as a replacement for systemic steroids. This would represent a significant shift and improvement in the current post-operative management of CRS. Patients would avoid the innumerable side effects of oral steroids, which are detailed above. Furthermore, while oral steroid usage is often limited by unwanted side effects, a topical regimen may be sustained over a prolonged period as a maintenance therapy if symptoms necessitate.

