Screening will be performed during clinic visits. First, it must be determined if a patient is a surgical candidate, which is a decision based on establishing the diagnosis of chronic rhinosinusitis by published diagnostic criteria. Furthermore, patients with this diagnosis must have failed maximum medical therapy. At the pre-operative appointment, a complete routine history will be taken as is standard in our clinics. This will include information regarding past medical history, past surgical history, current medications, social history, family history, and allergies. This information is readily available to us as a part of the electronic medical record. Patients must also confirm accuracy by filling out a questionnaire prior to their first encounter. No qualifying laboratory values are necessary.

j. Participation in Multiple Protocols

We do not anticipate that participants will be enrolled in more than one study. However, we will be sure to inquire before enrolling patients if they are actively participating in another study. If so, and our interventions may interfere in any way, we will not continue with the enrollment

process. We do not anticipate difficulty in recruiting the required number of patients, and, therefore, will defer to studies in which patients are already enrolled.

k. Payments to Participants

NA

l. Costs to Participants

The participant will accrue identical costs to any patient being evaluated and treated for chronic rhinosinusitis, which will vary tremendously based on insurance policies. During the process, costs that may accumulate include: clinic appointments, prescribed medications, surgical intervention, specialty evaluation. No additional costs will be charged based on participation in this study.

m. Planned Duration of the Study

The study duration is anticipated to be 12 months. Time allotted for screening of the participant will depend heavily on the time that elapses between the initial patient encounter in clinic and the date for which surgery is scheduled. This may require 1-6 months, and occasionally longer. Active study participation will begin at the surgical date and end at the 4th post-operative visit. Organization and analysis of the data will require 2-4 weeks.

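### The protocol's official 4-week comparison has no visit in its 2a schedule and is not carried into the SAP, which tests each score at four times with no primary score or multiplicity control

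*Protocol*

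**What the plan says.** **Official time.** Protocol 2g (Study Endpoint(s)) and, in the same words, 6e-iv (stopping rules): "We will use the final scheduled appointment at 4 weeks after surgery as the official end point for comparison of treatment arms".

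**Visits.** Protocol 2a (Procedures) schedules: "Post-operative visit 1: 1-2 weeks Post-operative visit 2: 6-8 weeks Post-operative visit 3: 12-16 weeks Post-operative visit 4: 6 months". It adds: "Study patients will attend post-operative appointments at identical time points to non-study patients". Section 2g instead gives usual care as 1, 3 and 6 weeks and says: "We will only slightly alter this timeline for study patients". Section 6c lists visits at 1, 2 and 4 weeks, and 2f speaks of clinic follow-up continuing after week 4. Section 5m says: "Active study participation will begin at the surgical date and end at the 4th post-operative visit", and 6d agrees.

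**Outcomes.** Section 2g names two, unranked: "outcomes evaluated will be the symptom questionnaire and the endoscopic exam score at each visit".

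**SAP.** Scores are collected at baseline and at 1 week, 1 month, 3 months and 6 months. SNOT-22 total, SNOT-22 subdomains, Lund-Kennedy and adverse effects are compared between arms by t-test at every time. No time or score is ranked. No significance level, assessment window or multiplicity rule is given. The text is in the past tense.

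**Early ending.** Sections 2g and 6e-iv: "If there is a clearly optimal therapy determined in these first 50 patients, we will end our research at that time". No boundary is stated. Section 6d places this look after the first 50 patients complete study therapy.

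**The concern.** A trial needs one comparison, fixed in advance, that answers its question. The protocol comes close by naming a time, but its own 2a schedule provides no assessment then, and it does not say which of two scores decides. The SAP, which should settle both matters, mentions neither. It adds subdomains that the protocol does not name and applies the same test to everything at every time.

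Two things are at stake. First, a reader cannot tell which data are the official ones: week 4, the SAP's 1 month, or a 2a visit. Second, if whichever score turns out significant can be presented as the result, the false-positive chance is well above the level of a single test. The protocol hopes the result will influence practice guidelines, so the deciding comparison should be identifiable.

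**Working it through.** **1. Assessment times side by side**

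| Source | Postoperative times | Near week 4? | Last visit |
|---|---|---|---|
| 2a | 1-2 wk, 6-8 wk, 12-16 wk, 6 mo | No | 6 months |
| 2g, 6e-iv | week 2; week 4 as the final appointment | Yes | 4 weeks |
| 6c | 1, 2, 4 wk | Yes | 4 weeks |
| 5m, 6d | participation ends at a 4th visit | not stated | 4th visit (6 months under 2a) |
| SAP | 1 wk, 1 mo, 3 mo, 6 mo | Yes | 6 months |

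One month is 365.25 / 12 / 7 = 4.35 weeks, which lies between 2a's first two windows. The SAP's four times match 2a's four visits in order except at the second, where the SAP has 1 month and 2a has 6-8 weeks. No window is given that would settle which it was. Section 6c lists only three visits and may concern safety monitoring alone, so the main conflict is 2a against 2g.

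**2. The plan's own figure.** Both documents say a power analysis requires 50 patients. This cannot be reproduced, because no outcome, time, effect, SD, level or power is given. Back-solving at 25 per arm, two-sided 0.05 and 80% power: (1.960 + 0.842) x sqrt(2/25) = 0.79 SD. It does not show which score or time was meant.

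**3. False positives.** Assumptions, none stated in the documents: no true difference, two-sided 0.05 per test, and one significant score is presented as the result. Ranges come from simulation of correlated normal statistics.

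- *Two protocol scores at the official time.* Independent: 1 - 0.95^2 = 0.0975. At correlation 0.5: 0.091. Range 9.1-9.8%, of which 4.5-4.9% would favour prednisone. With Holm: 4.6-4.9%.
- *Both scores at all four times (8 tests).* Independent: 1 - 0.95^8 = 0.337. With correlations of 0.3-0.5 between scores and 0.5-0.7 between visits: 23-28%, of which 11-14% would favour prednisone. This applies only if 2g's 4-week end point is not binding.
- Subdomains would add to the second figure. Their number is not in the documents, so none is given. Adverse-effect tests are not counted.

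**4. The 50-patient look, only if efficacy were tested there at 0.05.** With the same end point at 50 and 75 patients (information 50/75 = 2/3) and score correlation 0.5 to 0, two scores give 14-15% unadjusted and 7-8% with Holm at each look. Splitting the level as 0.001 at 50 and 0.049 at 75, with Holm within each look, gives 4.6-4.8%.

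**5. Power cost of Holm** (75 patients split 38/37, no dropout, noncentral t). The difference detectable with 80% power is 0.656 SD at 0.05 and 0.725 SD at 0.025, Holm's first step. With 50 patients it is 0.809 and 0.896 SD. For a 0.656 SD difference with 75 patients:

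- only one score differs: power falls from 0.800 to about 0.708;
- both differ, scores uncorrelated: 0.708 + (0.800 - 0.708) x 0.708 = 0.773 per score. Simulated t-tests at correlation 0.5 give 0.764. A normal approximation gives about 0.78.

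**The case against.** The strongest reply is that the protocol does fix the time. Sections 2g and 6e-iv call it official, 2f and 6c fit it, and the SAP collects 1-month scores. A short SAP that does not repeat a protocol statement has not revoked it, and 2a is the outlier. This largely stands. It makes the two-score figure the base case, but it does not rank the scores, give the 1-month assessment a window, or reconcile 2a.

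A second reply is that error is inflated only if one significant score counts as success, which neither document says. If both had to be significant, there would be no inflation (0.05^2 = 0.25% for independent scores). That is correct, but no such rule is written either. The 9-10% is therefore conditional on how a result would be presented.

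Four stronger readings are tempting and not supported:

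- *That no 4-week data exist.* This follows from 2a alone. The SAP says 1-month scores were collected.
- *That the trial's error rate is 23-28%.* This requires setting 2g aside.
- *That the 50-patient look is a second 0.05 test.* The documents speak only of clear or drastic superiority, with no threshold. The 14-15% depends on an assumed rule and on using the same end point at both looks, whereas 6d allows the look before all 50 patients reach week 4.
- *That the past tense shows outcomes were chosen after the data were seen.* It raises the question without answering it.

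The hope in Background 3a, "Could these be proven equally effective, topically delivered steroids may be considered as a replacement for systemic steroids", raises the lack of an equivalence margin. That is a separate point and adds nothing to the size of this one.

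**Conclusion.** The concern holds in this form. The 2a schedule conflicts with the official 4-week comparison in 2g and 6e-iv. The SAP carries over neither that time nor any rule for choosing between, or adjusting for, the two protocol scores, while testing both scores and the subdomains at four postoperative times.

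With the protocol's time treated as binding, the false-positive chance is about 9-10%, roughly twice nominal. This rests on an assumed two-sided 0.05 per test and on one significant score being presented as the result. About 23-28% is the outer case, reached only if the 4-week end point is not binding and under the assumed correlations. The schedule conflict and the absence of a primary score rest on the text alone and need no assumption.

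**What to change.** 1. Reconcile the assessment times in 2a, 2f, 2g, 5m, 6c, 6d, 6e-iv and the SAP, and state the window of the 4-week/1-month assessment.
2. In the SAP, make that time the single primary comparison. Then either name one primary score, with the choice dated and justified because the documents do not rank them, or use wording such as:

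> SNOT-22 total and Lund-Kennedy are compared between arms at the 4-week/1-month assessment, with Holm adjustment to an overall two-sided 0.05. Other times, and the subdomains at every time, are exploratory and reported as estimates with 95% confidence intervals.

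3. State whether outcome data had been seen when this choice was made. If so, label it post hoc.
4. State whether efficacy was tested at the 50-patient look. If it was, split the 0.05 across looks and report both levels; 0.001 and 0.049 is one workable split.

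The SAP's adverse-effect comparison is left as it is.

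**Cost.** Wording in the SAP and a protocol clarification, with no new data if 1-month scores were collected as stated. Results at other times and on subdomains are no longer confirmatory. With 75 patients, Holm lowers power for a 0.66 SD difference from 80% to 71% if only one score differs, or to about 76-77% per score if both do (about 78% by normal approximation). Naming one primary score avoids that loss but gives up a confirmatory claim on the other. If outcome data had already been seen, the change limits what may be claimed but cannot restore pre-specification.
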